7.3.2. Evaluation of Causality

Relationship of AEs to Study Drug:

The relationship of AEs to study drug will be assessed by the investigator and will be a clinical decision based on all available information. The following question will be addressed:

Is there a reasonable possibility that the AE may have been caused by the study drug?

The possible answers are:

Not Related: There is no reasonable possibility that the event may have been caused by the study drug

Related: There is a reasonable possibility that the event may have been caused by the study drug

The investigator should justify the causality assessment of each reported SAE.

Appendix 8 lists factors to consider in assessing the relationship of AEs to cemiplimab.

Relationship of Adverse Events to Study Conduct:

The relationship of AEs or SAEs to study conduct will be assessed by the investigator and will be a clinical decision based on all available information. The following question will be addressed:

Is there a reasonable possibility that the AE or SAE may have been caused by study conduct?

The possible answers are:

Not Related: There is no reasonable possibility that the event may have been caused by study conduct

Related: There is a reasonable possibility that the event may have been caused by study conduct.

A list of factors to consider when assessing the relationship of AEs or SAEs to study conduct is provided in Appendix 8.

The investigator should justify the causality assessment of each SAE.

7.4. Safety Monitoring

The investigator will monitor the safety of study patients at his/her site(s) as per the requirements of this protocol and consistent with current Good Clinical Practice (GCP). Any questions or concerns should be discussed with the sponsor in a timely fashion. The sponsor will monitor the safety data from across all study sites. The medical monitor will have primary responsibility for the emerging safety profile of the compound. The study monitor will be supported by other departments (eg, Pharmacovigilance and Risk Management; Biostatistics and Data Management). Safety monitoring will be performed on an ongoing basis (eg, individual review of SAEs) and on a periodic cumulative aggregate basis.

7.5. Investigator Alert Notification

Regeneron (or designee) will inform all investigators participating in this clinical trial, as well as in any other clinical trial using the same investigational drug, of any SAE that meets the relevant requirements for expedited reporting (an AE that is serious, unexpected based on the Investigator's Brochure, and has a reasonable suspected causal relationship to the medicinal/study drug).

8. STUDY VARIABLES AND ENDPOINTS

8.1. Demographic and Baseline Characteristics

Baseline characteristics will include standard demography (eg, age, race, weight, height), disease characteristics including medical history, cancer stage ([Edge 2010](#)), and medication history for each patient.

8.2. Primary and Secondary Endpoints

8.2.1. Primary Efficacy Endpoints

The primary efficacy endpoint for this study is ORR according to central review during the 12 treatment cycles (Groups 1, 2, and 6), or 6 treatment cycles (Groups 3 and 4). Overall response rate will be assessed separately for patients with metastatic CSCC or locally advanced CSCC:

- For patients with metastatic disease, RECIST version 1.1 will be used to determine ORR ([Eisenhauer 2009](#)) ([Appendix 1](#)). Patients in which all response assessments are performed on radiologic scans according to RECIST 1.1, the determination of the independent radiologic response assessment committee will serve as the central response assessment. Clinical or composite response criteria ([Appendix 2](#)) may be used for patients with externally visible target lesions, if all metastatic lesions are not measurable by RECIST (such as may occur in patients with bone-only metastases).
- For patients with unresectable locally advanced disease, clinical response criteria ([Appendix 1](#)) will be used to determine ORR, for externally visible tumor(s) use bi-dimensional measurements according to World Health Organization (WHO) criteria. Composite response criteria will be used for patients who have both target lesions measurable by clinical response criteria and by RECIST 1.1 to determine ORR ([Appendix 2](#)). In patients achieving a CR, tumor biopsies will be used in the final determination of complete versus PR.

Patients who are deemed not evaluable (NE) by RECIST version 1.1 (Groups 1, 3, 4, and 6; [Appendix 1](#)) or inevaluable by the clinical or composite response criteria (Group 2; [Appendix 2](#)) will be considered as not reaching PR/CR for ORR. ORR will be calculated from time of enrollment.

8.2.2. Secondary Endpoints

The secondary efficacy endpoints are:

- ORR for Groups 1 through 6 by investigator assessments:
 - For patients with metastatic CSCC in which all response assessments are performed on radiologic scans according to RECIST 1.1, the term “composite response assessment” is not applicable. The investigator’s response assessment for such patients will be RECIST 1.1 assessment.
 - For patients with locally advanced CSCC in which all response assessments are performed on photographs according to Clinical Response Criteria for Externally Visible Tumors (in [Appendix 2](#)), the term “composite response assessment” is not

applicable. The investigator’s response assessment for such patients will be according to Clinical Response Criteria for Externally Visible Tumors.

- For patients in which target lesion response assessments are performed with both scans (according to RECIST 1.1) and photographs (according to Clinical Response Criteria for Externally Visible Tumors), the investigator’s response assessment will be according to Composite Response Criteria (in [Appendix 3](#)).
- DOR – measured from the time measurement criteria are first met for CR/PR, whichever is recorded first, until the first date of recurrent or progressive disease or death due to any cause in patients with best overall response (BOR) of CR or PR
- PFS – measured from time of enrollment until the first date of recurrent or progressive disease, or death due to any cause
- OS – measured from time of enrollment until death due to any cause
- CR rate
- Change in scores of patient-reported outcomes on EORTC QLQ-C30 (except Group 6)
- AEs
- Cemiplimab concentrations in serum ([Appendix 3](#))
- Anti-drug antibodies (ADA)
- For Group 6 only: To assess relationships between PD-L1 status (by IHC) and efficacy measures (ORR, DOR, PFS).

8.2.3. Exploratory Endpoints

The following exploratory analyses are planned:

- [REDACTED]
- [REDACTED]
- [REDACTED]
- [REDACTED]
- [REDACTED]
- [REDACTED]
- [REDACTED]
- [REDACTED]
- [REDACTED]
- [REDACTED]

8.2.4. Pharmacokinetic Variables

Serum concentration of cemiplimab will be assessed at multiple time points throughout the study treatment and follow-up periods, and the PK will be analyzed.

Pharmacokinetic variables may include, but are not limited to, the following:

- C_{eoi} – concentration at end-of-infusion (IV)
- C_{max} – peak concentration (SC)
- C_{trough} – pre-infusion concentration
- t_{eoi} – time of end-of-infusion
- t_{max} – time to peak concentration (SC)
- $\text{AUC}_{3\text{w}}$ – area under the plasma concentration-time curve after the first SC or IV dose
- F – Absolute bioavailability after SC administration

8.3. Anti-Drug Antibody Variables

Regeneron plans to evaluate the impact of the immunogenicity of cemiplimab.

Anti-drug antibody variables include ADA status and titer as follows:

- Treatment emergent – defined as any positive postdose ADA assay response when baseline results are negative
- Treatment boosted – defined as any postdose ADA response that is at least 9-fold over baseline titer levels
- Titer values (Titer value category):
 - Low (titer <1,000)
 - Moderate ($1,000 \leq \text{titer} \leq 10,000$)
 - High (titer >10,000)

The relationship between immunogenicity and PK of cemiplimab may be assessed, as appropriate.

8.4. Exploratory Biomarker Variables – Group 6

Exploratory pharmacodynamic and biomarker variables for Group 6 include:

- [REDACTED]
- [REDACTED]
- [REDACTED]
- [REDACTED]
- [REDACTED]
- [REDACTED]

9. STATISTICAL PLAN

This section provides the basis for the statistical analysis plan (SAP) for the study. The SAP may be revised during the study to accommodate amendments to the clinical study protocol and to make changes to adapt to unexpected issues in study execution and data that may affect the planned analyses. The SAP will be issued before the database is locked.

Analysis variables are listed in Section 8.

9.1. Statistical Hypothesis

For the primary endpoint of ORR, the following null hypothesis and alternative will be tested for Groups 1, 2, 3, 4, and 6, respectively.

Group 1: H_0 : ORR = 15% vs. H_1 : ORR \neq 15%

Group 2: H_0 : ORR = 25% vs. H_1 : ORR \neq 25%

Group 3: H_0 : ORR = 15% vs. H_1 : ORR \neq 15%

Group 4: H_0 : ORR = 20% vs. H_1 : ORR \neq 20%

Group 6: H_0 : ORR = 28% vs. H_1 : ORR \neq 28%

9.2. Justification of Sample Size

Patients will be enrolled into 6 separate groups. A single-stage exact binomial design is adopted for Groups 1, 2, 3, 4, and 6 respectively, for the primary endpoint of ORR. After completion of enrollment in Group 1, up to 53 additional patients with metastatic CSCC will be enrolled in Group 3. Group 4 will begin enrollment after completion of enrollment in Groups 1 through 3.

Published clinical studies for CSCC patients have had relatively small sample sizes and often include a wide range of disease stages (Nakamura 2013). Clinical studies of CSCC patients have been predominantly composed of patients with locally advanced disease (primary site). The NCCN guidelines for CSCC, cisplatin monotherapy, cisplatin plus 5-FU, and cetuximab are described as “possible options” (Bichakjian 2015). In the only study of cisplatin-based therapy for advanced CSCC reported in the last 15 years, the ORR was 34% (Shin 2002). Cetuximab yielded a response rate of 28% in a phase 2 study for patients with advanced CSCC (Maubec 2011). Most patients in these studies had locoregionally advanced disease. There hasn't been a publication of a clinical study specifically for patients with metastatic CSCC. The aggregate experience of patients enrolled in trials of systemic therapy indicates that a clinically meaningful ORR for an investigational agent would be >15% for patients with metastatic disease or >25% for patients with unresectable locally/regionally advanced CSCC (Khansur 1991, Lippman 1992, Nakamura 2013, Shin 2002).

Group 4 enrolls patients with advanced CSCC (metastatic or locally advanced). The clinically meaningful ORR would range from 15% to 25% for patients with advanced CSCC. Assuming equal number of patients with metastatic CSCC or locally advanced CSCC, the clinically meaningful ORR would be >20% for patients with advanced CSCC. (Note: With protocol Amendment 7, enrollment will begin for Group 6 and enrollment for Group 4 will close even if it is not fully enrolled. If statistical hypothesis testing for Group 4 is not possible due to incomplete enrollment, descriptive statistics will be used for Group 4).

Hence, the sample sizes for Group 1 through 4 were selected such that the lower limit of the 95% confidence intervals of the estimated ORRs will be clinically meaningful. The non-clinically meaningful ORR of 15% for Group 1 and Group 3 (evaluated independently) will be excluded using the lower limit of 95% CI if the observed ORR is 28.0% or more; ie, the ORR for Group 1 and/or Group 3 (evaluated independently) is significantly different from 15%. The non-clinically meaningful ORR of 25% for Group 2 will be excluded using the lower limit of 95% CI if the observed ORR is 36.1% or more (ie, the ORR for Group 2 is significantly different from 25%). The non-clinically meaningful ORR of 20% for Group 4 will be excluded using the lower limit of 95% confidence interval if the observed ORR is 31.7% or more; ie, the ORR for Group 4 is significantly different from 20%. In addition, if the observed ORR for Group 4 is 26.7% or 38.3% or more, the ORR for Group 4 is significantly different from 15% or 25% respectively, using the lower limit of the 95% confidence intervals (see [Table 10](#), [Table 11](#), and [Table 12](#)).

Group 6 enrolls patients with advanced CSCC (metastatic or locally advanced). The statistical design for Group 6 will be capable of demonstrating a point estimate of ORR (per independent central review) in which the lower bound of the 95% confidence interval excludes the highest centrally reviewed ORR in the literature for any prospective study of systemic anticancer treatment (other than cemiplimab) that enrolled at least 30 patients. Most previous studies of advanced CSCC used investigator-based assessments of ORR ([William 2017](#), [Gold 2018](#), [Shin 2002](#), [Lippman 1992](#), [Khansur 1991](#), [Sadek 1990](#), [Cartei 2000](#)) and therefore do not serve as comparators for ORR per independent central review in Study 1540. Additionally, some studies did not report results according to intention-to-treat ([Shin 2002](#), [Lippman 1992](#), [Sadek 1990](#)). However, the phase 2 study of cetuximab (N = 36 patients) in advanced CSCC did report ORR of 28% per independent radiology review ([Maubec 2011](#)). As such, 28% is the highest reported ORR in any study in advanced CSCC patients that used independent radiology review and enrolled at least 30 patients. The statistical plan for Group 6 is capable of testing for an ORR (per independent central review) that excludes 28% at the lower bound of the 95% confidence interval.

Table 10: The 95% Binomial Exact Confidence Intervals for Observed ORR in Group 1 and Group 3 Given a Sample Size of 50 Patients (Based on 85% Power)

Number of Responders	Observed ORR	95%CI – lower	95% CI – upper
7	0.14	0.058	0.267
8	0.16	0.072	0.291
9	0.18	0.086	0.314
10	0.20	0.100	0.337
11	0.22	0.115	0.360
12	0.24	0.131	0.382
13	0.26	0.146	0.403
14	0.28	0.162	0.425
15	0.30	0.179	0.446
16	0.32	0.195	0.467
17	0.34	0.212	0.488

Table 11: The 95% Binomial Exact Confidence Intervals for Observed ORR in Group 2 Given a Sample Size of 72 Patients (Based on 90% Power)

Number of Responders	Observed ORR	95%CI – lower	95% CI – upper
18	0.250	0.155	0.366
19	0.264	0.167	0.381
20	0.278	0.179	0.396
21	0.292	0.190	0.411
22	0.306	0.202	0.425
23	0.319	0.214	0.440
24	0.333	0.227	0.454
25	0.347	0.239	0.469
26	0.361	0.251	0.483
27	0.375	0.264	0.497
28	0.389	0.276	0.511
29	0.403	0.289	0.525
30	0.417	0.302	0.539
31	0.431	0.314	0.553
32	0.444	0.327	0.566

Table 12: The 95% Binomial Exact Confidence Intervals for Observed ORR in Group 4 Given a Sample Size of 60 Patients (Based on 92% Power)

Number of Responders	Observed ORR	95%CI – lower	95% CI – upper
16	0.267	0.161	0.397
19	0.317	0.203	0.450
23	0.383	0.261	0.518
26	0.433	0.306	0.568

For Groups 1 and 3, 50 patients (in each group) will be required to provide at least 85% power to reject a null hypothesis of an ORR of 15% at a 2-sided significance level of no more than 5% if the true ORR is 34%. For Group 2, 72 patients will be required to provide at least 90% power to reject a null hypothesis of an ORR of 25% at a 2-sided significance level of no more than 5% if the true ORR is 44%. For Group 4, 60 patients with advanced CSCC will be required to provide at least 92% power to reject a null hypothesis of an ORR of 20% at a 2-sided significance level of no more than 5% if the true ORR is 40%. In addition, for Group 4, 60 patients with advanced CSCC will provide at least 93% or 87% power to reject a null hypothesis of an ORR of 15% or 25% at a 2-sided significance level of no more than 5% if true ORR is 35% or 45% respectively. The sample sizes will be further increased by 5% to account for patients who withdraw prematurely from the study. Hence, the total planned sample sizes will be 53 patients (actual enrolled 59) for Group 1, 76 patients (actual enrolled 78) for Group 2, 53 patients (actual enrolled 56) in Group 3, and 63 patients for Group 4.

Group 5 is a pilot cohort to obtain initial clinical and PK experience among patients who receive a single dose of cemiplimab SC, with a sample size of 10 patients for PK analysis.

The sample size for Group 6 was selected such that the lower limit of the 95% confidence interval of the estimated ORR excludes the highest independently-reviewed ORR to date in any prospective study of anticancer systemic therapy for advanced CSCC that enrolled at least 30 patients.

For Group 6, 150 patients will be required to provide at least 85% power to reject a null hypothesis of an ORR of 28% at a 2-sided significance level of no more than 5% if the true ORR is 40%. The sample size will be further increased by 10% to account for patients who withdraw prematurely from the study. Hence, the total planned sample size will be approximately 167 patients for Group 6. The ORR of 28% for Group 6 will be excluded using the lower limit of 95% exact CI if the observed ORR is 35.3% or more, ie, the ORR for Group 6 is significantly different from 28% (Table 13).

Table 13: The 95% Binomial Exact Confidence Intervals for Observed ORR in Group 6 Given a Sample Size of 167 Patients

Number of Responders	Observed ORR	95%CI – lower	95% CI – upper
56	33.5%	26.4%	41.2%
57	34.1%	27.0%	41.9%
58	34.7%	27.5%	42.5%
59	35.3%	28.1%	43.1%
60	35.9%	28.7%	43.7%
61	36.5%	29.2%	44.3%
62	37.1%	29.8%	44.9%

In Group 6, enrollment of metastatic CSCC patients will be capped at 133 patients to allow for at least 34 patients with locally advanced CSCC to be enrolled. This mirrors the real-world distribution of metastatic (80%) and locally advanced (20%) patients with CSCC described in retrospective study of advanced CSCC in the US Oncology Network (Cowey, manuscript in preparation). [Appendix 10](#) presents reference tables for Group 6 subgroup analyses. However, the primary analysis for Group 6 is based on all advanced CSCC patients, both metastatic and locally advanced. These subgroup analyses are descriptive only.

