9.3. Analysis Sets

9.3.1. Full Analysis Set

The full analysis set (FAS) includes all patients who have passed screening and deemed to be eligible for this study. All efficacy endpoints will be analyzed using FAS.

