APPENDIX 10. STATISTICAL ANALYSES

ESTIMANDS

For Group 6 primary analysis, the statistical methods for the primary and secondary endpoints will be consistent with that which was done for Groups 1 to 3. This will facilitate a meaningful comparison of Group 6 with the previous groups. Additional statistical analyses will also be performed, including sensitivity analyses for DOR and PFS assuming informative censoring for intercurrent event.

Attributes for ORR per Central Review and Investigator Assessment

1. The study population is defined as CSCC patients who are enrolled on the protocol.
2. The endpoint is ORR, defined as the proportion of patients with BOR of CR or PR. ORR per central review is the primary endpoint, and ORR per investigator assessment is a secondary endpoint.
3. Intercurrent events and how to account for these events are described in [Table 16](#).
4. Estimated ORR will be provided, along with the 2-sided 95% exact binomial confidence interval using the Clopper-Pearson method.

Table 16: Intercurrent Events for Analysis of ORR per Central Review and Investigator Assessment

Intercurrent events	Rules of imputing data in primary analysis
Initiation of palliative radiation therapy	Patient will be considered to have PD at time of initiation of radiation (Section 5.7.4 of protocol).
Surgical removal of target lesion	BOR will be considered as PR if no prior PD is observed (Section 5.7.3 of protocol).
Unconventional responses (eg, a patient first experience PD and then CR or PR)	BOR will be considered as PD.
No evaluable postbaseline tumor assessment	BOR will be deemed NE. Patient with BOR of NE will be included in the ORR analysis as a non-responder.

A sensitivity analysis will be performed for ORR where the intercurrent events of “initiation of palliative radiation therapy” and “surgical removal of target lesion” will be ignored. Patients with unconventional responses will be considered as responders. Patients with BOR of NE will be excluded from this analysis.

Attributes for DOR per Central Review and Investigator Assessment

1. The study population is defined as CSCC patients who are enrolled on the protocol and had a CR/PR response.
2. The endpoint is DOR, measured from the time measurement criteria are first met for CR/PR (whichever is first recorded) until the first date of recurrent or progressive disease or death due to any cause in patients with BOR of CR or PR.

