For Group 6, the rates of intercurrent events are expected to be similar to those observed in Groups 1 to 3. Frequencies of these events in Groups 1 to 3 are presented in [Table 20](#).

Table 20: Frequency of Intercurrent Events in Group 1, 2, and 3 in the Primary Analysis

Intercurrent event	Endpoint	Group 1 (N=59)	Group 2 (N=78)	Group 3 (N=56)
Initiation of radiation therapy	ORR, DOR, PFS	0	0	0
Surgical removal of target lesion	ORR, DOR	1 (1.7%)	0	0
Unconventional response	ORR, DOR, PFS	0	2 (2.6%)	0
No evaluable post-baseline tumor assessment (BOR=NE)	ORR, DOR	7 (11.9%)	7 (9.0%)	6 (10.7%)
Due to early death	PFS	3 (5.1%)	1 (1.3%)	3 (5.4%)
Due to reasons other than death	PFS	4 (6.8%)	6 (7.7%)	3 (5.4%)
Lost to follow-up or Discontinuation of study in patients with BOR of CR or PR	DOR	1 (1.7%)	11 (14.1%)	1 (1.8%)
Due to AE or PD	DOR	1 (1.7%)	1 (1.3%)	0

Intercurrent event	Endpoint	Group 1 (N=59)	Group 2 (N=78)	Group 3 (N=56)
Lost to follow-up or Discontinuation of study after at least one evaluable post-baseline tumor assessment	PFS	15 (25.4%)	35 (44.9%)	19 (33.9%)
Due to AE or PD	PFS	12 (20.3%)	14 (17.9%)	14 (25.0%)
New anti-cancer therapy added	OS	8 (13.6%)	5 (6.4%)	8 (14.3%)
Lost to survival follow up	OS	6 (10.2%)	33 (42.3%)	13 (23.2%)

SUBGROUP ANALYSES – METASTATIC AND LOCALLY ADVANCED CSCC PATIENTS AT FINAL ANALYSIS

Table 21 and Table 22 provide the 95% confidence intervals for observed ORRs for the 2 subgroups of Group 6: metastatic and locally advanced CSCC separately. The primary analysis for Group 6 is based on all advanced CSCC patients, both metastatic and locally advanced. These subgroup analyses are descriptive only.

Table 21: The Binomial Exact Confidence Intervals for Observed ORR in Metastatic CSCC Patients at Final Analysis (N=133)

Number of Responders	ORR (N=133)	95% CI (%)
47	35.3%	(27.3, 44.1)
48	36.1%	(27.9, 44.9)
49	36.8%	(28.6, 45.6)
50	37.6%	(29.3, 46.4)
51	38.3%	(30.1, 47.2)
52	39.1%	(30.8, 47.9)
53	39.8%	(31.5, 48.7)
54	40.6%	(32.2, 49.5)
55	41.4%	(32.9, 50.2)
56	42.1%	(33.6, 51.0)
57	42.9%	(34.3, 51.7)
58	43.6%	(35.0, 52.5)
59	44.4%	(35.8, 53.2)
60	45.1%	(36.5, 54.0)

Table 22: The Binomial Exact Confidence Intervals for Observed ORR in Locally Advanced CSCC Patients at Final Analysis (N=34)

Number of Responders	ORR (N=34)	95% CI (%)
11	32.4%	(17.4, 50.5)
12	35.3%	(19.7, 53.5)
13	38.2%	(22.2, 56.4)
14	41.2%	(24.6, 59.3)
15	44.1%	(27.2, 62.1)

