4.5. Efficacy Variable

4.5.1. Primary Efficacy Variable

Overall response is based on **central-reviewed evaluation** at each time point at which a response assessment occurs using the RECIST version 1.1 (Appendix 1 of the protocol) or the composite response criteria (Appendix 2 of the protocol).

Best overall response (BOR) is determined once all the overall response data for the patient are known. The best overall response is the best response recorded during the study.

- Best overall response of CR or PR must be confirmed by consecutive evaluations of overall response of CR or PR at time points at least 4 weeks apart. In addition, locally advanced CSCC patients followed by digital medical photography require biopsy to confirm CR.
- Best overall response of SD must have met the response SD criteria at least once ≥ 39 days (6 weeks*7 days/week -3 days) after start of study treatment. Best overall

response of (early) PD does not require confirmation using the RECIST or the composite response criteria.

- The best overall response for patients who do not have any post-baseline tumor assessment will be not evaluable (NE). Patients with best overall response of NE will be considered as not reaching an objective response of CR or PR.

Objective response rate (ORR) is determined by the proportion of patients with best overall response of CR or PR in the FAS by group.

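### Does adding 10% to Group 6 for withdrawals leave it underpowered, given that withdrawn patients stay in the ORR denominator?

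*Protocol*

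**What the plan says.** Protocol 9.2 states that "150 patients will be required to provide at least 85% power to reject a null hypothesis of an ORR of 28" per cent, two-sided at 5%, if the true ORR is 40%. It then says: "The sample size will be further increased by 10% to account for patients who withdraw prematurely from the study", which gives approximately 167. SAP 2.2 repeats both statements. Protocol 9.2 and its Table 13 set success at an observed ORR of 35.3%, which is 59 of 167. SAP Table 2 gives the same count for the 95.10% interval used at the final analysis where alpha spending applies.

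The analysis rules are clear:
- Protocol 9.3.1: "All efficacy endpoints will be analyzed using FAS". That set is all patients who passed screening and were deemed eligible.
- SAP 4.5.1: "Objective response rate (ORR) is determined by the proportion of patients with best overall response of CR or PR in the FAS by group".
- Protocol Appendix 10, Table 16: "Patient with BOR of NE will be included in the ORR analysis as a non-responder". SAP 6.2 confirms that such patients stay in the denominator.
- SAP 4.5.1 also requires CR or PR to be confirmed at least 4 weeks later, so a patient lost before confirmation is not a responder.

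Protocol 9.1 introduces the hypotheses this way: "For the primary endpoint of ORR, the following null hypothesis and alternative will be tested". Appendix 10 adds: "For Group 6, the rates of intercurrent events are expected to be similar to those observed in Groups 1 to 3".

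**The concern.** An allowance of the form n/(1 − d) is meant for an analysis of those who remain: enrol 167, lose 10%, analyse about 150, and keep the power worked out for 150. In this plan nobody leaves the primary denominator. A patient lost before a confirmed response becomes a non-responder, so losses lower the response rate while the threshold stays at 59 of 167. A reader could take the sentence to mean that 10% withdrawal has been paid for.

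If it has not, a group that supports a regulatory commitment could have well under 85% power without the plan saying so. The allowance of 5% for Groups 1 to 4 has the same form, so the question reaches beyond Group 6.

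**Working it through.** **Inputs.** Null ORR 28%, alternative 40%, two-sided 5%, base size 150, inflation 10%, planned size 167 (Protocol 9.2). Intervals are Clopper-Pearson (Protocol 9.5.2). Loss counts come from Protocol Appendix 10, Table 20.

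**Method.** The critical count r is the smallest number of responders whose lower 95% limit exceeds 28%. Power is P(X ≥ r) for X ~ Binomial(N, p).

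**1. The plan's own figures.**
- N = 150: r = 54, and P(X ≥ 54 | p = 0.40) = 86.1%. The statement of at least 85% holds.
- 150 / 0.90 = 166.7, which rounds up to 167.
- N = 167: 59 responders (35.3%) give a lower limit of 28.1%; 58 give 27.5% and fail. This agrees with Table 13. The critical count is still 59 with the 95.10% interval.

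**2. If 40% is the ORR in the full analysis set.** Non-response through withdrawal is already inside the 40%.
- P(X ≥ 59 | N = 167, p = 0.40) = 90.6%. The 17 extra patients add 90.6 − 86.1 = 4.5 points of power.
- At the null, P(X ≥ 59 | p = 0.28) = 2.3%, within the 2.5% allowed in the upper tail.
- Power reaches 85% at p = 38.94%. It is 78.5% at 38%, 60.0% at 36% and 96.7% at 42%.

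**3. If 40% applied only to patients who stay.** With a share d lost before a confirmed response, the ORR in the full analysis set is 0.40 × (1 − d).

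| d | ORR, full analysis set | Power, N = 167 | Power, N = 150 |
|---|---|---|---|
| 0% | 40.0% | 90.6% | 86.1% |
| 2% | 39.2% | 86.6% | 81.2% |
| 5% | 38.0% | 78.5% | 72.0% |
| 10% | 36.0% | 60.0% | 53.1% |

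Power of 85% is kept up to d = 1 − 0.38939/0.40 = 2.7%. In counts, four such losses leave P(Binomial(163, 0.40) ≥ 59) = 85.8%; five leave 84.4%.

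**4. What Table 20 suggests about losses.** Patients with no evaluable post-baseline assessment for reasons other than death number 4 + 6 + 3 = 13 of 193 (59 + 78 + 56), or 6.7%. Put into step 3, this gives an ORR of 37.3% and power of 72.7%. The row "Lost to follow-up or Discontinuation of study in patients with BOR of CR or PR" shows another 1 + 11 + 1 = 13 of 193. Those patients had already responded and still count, so not every departure costs a response.

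**5. Groups 1 to 4 at planned size and stated ORR.**

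| Group | N | Responders needed | True ORR | Power | Stated |
|---|---|---|---|---|---|
| 1 and 3 | 53 | 14 | 34% | 90.7% | 85% |
| 2 | 76 | 28 | 44% | 91.6% | 90% |
| 4 | 63 | 20 | 40% | 93.0% | 92% |

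Every stated power is met.

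**The case for a change.** The best argument for a change is that neither reading of 40% makes the withdrawal sentence true. If 40% is the ORR in the full analysis set, withdrawals are already counted and the extra patients are simply more power. If 40% belongs to those who stay, 17 patients do not buy back a 10% loss. The power at 167 appears nowhere, and the reader is not told that a true ORR about 1 percentage point lower takes power below 85%. Group 2 shows how loosely the inflation and the power are linked: going from 72 to 76 patients moves the threshold from 26 to 28 and lowers exact power at 44% from 93.0% to 91.6%.

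The mismatch in the rationale stands, and so does the absence of a power figure at 167. The rest is weaker. The figures in step 3 depend on a meaning of 40% that no section gives, whereas Protocol 9.1 ties the hypotheses to the primary endpoint, which is defined on the full analysis set. The count of 13 in 193 measures evaluability; Table 20 does not say those patients withdrew. The narrow margin below 40% is a property of the power curve and would be the same with no withdrawals at all. It would also be too strong to say that the extra patients offset nothing, since on the less favourable reading they raise power from 72.0% to 78.5% at 5% loss. Finally, Appendix 10 plans a sensitivity analysis of ORR that leaves out patients who are not evaluable, and there an allowance of this form does its usual job.

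**Conclusion.** No change is needed. The withdrawal sentence gives a poor reason for a sample size that does no harm. The base power, the inflation and the success threshold all reproduce, and the 59-of-167 rule is already stated on the denominator that will be used. If 40% is the ORR in the full analysis set, power is 90.6% against the 85% promised, and Groups 1 to 4 also meet their stated powers at planned size.

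This conclusion rests on that meaning of 40%, which is the natural one but is not spelled out. If the sponsor meant patients who stay, the allowance covers about 2.7% loss before a confirmed response, and power would be 78.5% at 5% loss and 60.0% at 10%. Even then the decision rule, its type I error and the analysis would be the same. Rewording could only make the record neater. By Protocol 1.2.1, Amendment 9 takes effect only after the data cut for the Group 6 primary analyses, so the wording can no longer affect how many patients that analysis includes.
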